7.2 CLINICAL LABORATORY PARAMETERS	17
7.3 VITAL SIGNS AND PHYSICAL EXAMINATION FINDINGS	18
7.3.1 Vital Signs	18
7.3.2 Physical Examination	19
8. INTERIM ANALYSES AND DATA AND SAFETY MONITORING BOARD (DSMB)	19
8.1 INTERIM ANALYSES	19
8.2 DATA AND SAFETY MONITORING BOARD (DSMB)	19
9. SUMMARY OF MAJOR CHANGES IN THE PLANNED ANALYSES	19
10. APPENDICES	20
APPENDIX 1.1 ADVERSE EVENT SCALE	20
APPENDIX 1.2 PEDIATRIC VITAL SIGNS REFERENCE CHART	22

LIST OF ABBREVIATIONS AND DEFINITIONS

AE	Adverse Event
ALT	Alanine Aminotransferase
AST	Aspartate Aminotransferase
BUN	Blood Urea Nitrogen
CHr	Reticulocyte Hemoglobin Content
CTCAE	Common Terminology Criteria for Adverse Events
dl	Deciliter
eCRF	Electronic Case Report Form
e.g.	For Example
EOS	End of Study
FCM	Ferric Carboxymaltose
FDA	Food and Drug Administration
Fe	Iron
g	Gram
GCP	Good Clinical Practice
GGT	Gamma-Glutamyl Transferase
Hct	Hematocrit
HBsAg	Hepatitis B Surface Antigen
HCV	Hepatitis C Viral Antibody
Hgb	Hemoglobin
HIV	Human Immunodeficiency Virus
IBD	Inflammatory Bowel Disease
ICH	International Conference on Harmonisation
IDA	Iron-deficiency Anemia
i.e.	That Is
IND	Investigational New Drug Application
IRB	Institutional Review Board
IRT	Interactive Response Technology
IV	Intravenous
Kg	Kilogram
L	Liter
LDH	Lactate Dehydrogenase
MCH	Mean Cell Hemoglobin
MCHC	Mean Corpuscular Hemoglobin Concentration
MCV	Mean Corpuscular Volume
MedDRA	Medical Dictionary for Regulatory Activities
m	Meter
mg	Milligrams
mL	Milliliter
NCI	National Cancer Institute
ng	Nanogram
PCS	Potentially Clinically Significant
PE	Physical Examination

PT	Preferred Term
RBC	Red Blood Cells
RDW	Red Cell Distribution Width
SAE	Serious Adverse Event
SAP	Statistical Analysis Plan
SD	Standard Deviation
SOC	System Organ Class
TEAE	Treatment Emergent Adverse Event
TIBC	Total Iron Binding Capacity
TSAT	Transferrin Saturation
US	United States
WBC	White Blood Cells
WHO	World Health Organization

1. INTRODUCTION

The purpose of this statistical analysis plan (SAP) is to describe the procedures and the statistical methods that will be used to analyze and report results for Protocol 1VIT18045 (Administrative Change 1 Date: 03 December 2019). This SAP should be read in conjunction with the corresponding clinical study protocol and electronic case report forms (eCRFs).

1.1 STUDY OBJECTIVES

1.1.1 Primary Objective

The primary objective of this study is to evaluate the efficacy and safety of intravenous (IV) Ferric Carboxymaltose (FCM) in pediatric participants who have iron deficiency anemia (IDA).

1.2 STUDY ENDPOINTS

1.2.1 Primary Efficacy Endpoint

The primary endpoint is the change in hemoglobin (Hgb) from baseline to Day 35.

1.2.2 Secondary Efficacy Endpoints

Secondary efficacy endpoints include:

- Change in ferritin from baseline to Day 35
- Change in transferrin saturation (TSAT) from baseline to Day 35
- Changes from baseline in Hgb, ferritin, TSAT, and reticulocyte hemoglobin content (CHr) throughout the study.

1.2.3 Safety Endpoints

Safety endpoints include:

- Extent of exposure
- Adverse events
- Laboratory assessments
- Vital signs
- Physical examinations

1.3 SUMMARY OF THE STUDY DESIGN

1.3.1 General Study Design and Plan

This is a single arm, open-label, multi-center, multi-national, non-randomized study that will evaluate the efficacy and safety of a one course treatment with FCM in participants who had an unsatisfactory response to oral iron in study 1VIT17044.

Subjects will have an EOS Visit (Day 35) from the 1VIT17044 study to qualify for entry. Subjects will then be screened, meet all inclusion criteria, no exclusion criteria and have a baseline evaluation. Based on the successful completion of the baseline evaluations, subjects will be enrolled and will receive the first dose of FCM (Day 0). The second FCM dose should occur 7 days from the first dose. Subjects will return to the clinic 14 and 28 days post their first dose for laboratory and safety assessments, and at 35 days post the first dose, participants will return to the clinic for final safety and efficacy assessments. Once all assessments are complete the participant will exit the study.

An **unsatisfactory response** to oral iron (i.e., an increase in Hgb of <1 g/dL from baseline) will be defined as non-responders to oral iron treatment. Non-responders who continue to meet all inclusion criteria (including Hgb <11 g/dL) and none of the exclusion criteria will receive 1 course of FCM.

Table 1: Schedule of Activities

Procedures	Screening ¹ Day -7 to -1	Enrollment Visit 1, Day 0	Study Visit 2 Day 7 ± 1 day	Study Visit 3 Day 14 ± 1 day	Study Visit 4 Day 28 ± 1 day	Study Visit 5 Day 35 ± 1 day
Informed Consent / Assent	X					
Medical History	X					
Physical Exam		X				X
Inclusion/Exclusion Criteria	X	X				
IRT	X	X				X
Vital Signs	X	X	X	X	X	X
Weight	X	X				
Height	X					
Temperature		X	X			
Blood sampling for Hematology, Chemistry and Iron Indices (5.5 mL) ¹	X	X	X	X	X	X
Blood sampling for Serum Pregnancy Test (1.5 mL), if applicable	X					X
Concomitant Medications	X	X	X	X	X	X
Adverse Event Assessment		X	X	X	X	X
FCM Dosing		X	X			

1. Note that there will be a 7 ± 1 day waiting period between 1VIT17044 end of study and extension screening

2. For a full description of central laboratory assessments, refer to Protocol Section 6.4.

1.3.2 Stratification/Randomization

This is a non-randomized, single arm study.

1.3.3 Sample Size and Statistical Power Considerations

There were no sample size estimations for this study. The current study is a rollover for study 1VIT17044. There will be a maximum of approximately 36 participants from study 1VIT17044 who had an unsatisfactory response to oral iron or required an intervention.

2. STATISTICAL METHODS

2.1 GENERAL CONSIDERATIONS

Analysis datasets will be produced according to CDISC standards. All study-collected data will be summarized in tables or graphs. Listing will be produced when appropriate and all ICH-required listings will be produced.

Continuous variables will be summarized in terms of the number of observations (n), mean, standard deviation (SD), median, quartiles (Q1 and Q3), minimum (min), and maximum (max) values. Other descriptive statistics (e.g., coefficient of variation) may be reported when appropriate. Analysis of categorical variables will include frequency counts and percentages. Unknown and missing data may be presented as a separate category and the denominator will include unknown or missing values as appropriate. If applicable, hypothesis testing will be carried out at the two-sided $\alpha=0.05$ level unless otherwise specified; 2-sided 95% confidence intervals (CIs) will be presented, where specified.

Generally, data will be summarized by nominal visit. However, data from both unscheduled and scheduled will be used for determination of last observed value, and in worst- or best-case changes and/or shifts from baseline. Assessment windows will not be defined for the purpose of classifying measurements obtained outside scheduled assessment times.

2.1.1 Reporting Precision

Summary statistics will be presented to the following degree of precision, unless otherwise specified:

Statistics	Degree of Precision
Mean, Geometric mean, Median, Quartiles, Confidence limit boundaries	One decimal place more than the raw data.
Standard deviation, Standard error	Two decimal places more than the raw data.
Minimum, Maximum	The same as the raw data.
p-value	Rounded to 4 decimal places and therefore presented as 0. xxxx; p-values smaller than

	0.0001 as ‘<0.0001’; p-values greater than 0.9999 as ‘>0.9999’.
Percentage	One decimal place. A percentage of 100% will be reported as 100%. Percentages of zero will be reported as 0.

For weight and height, one decimal place will be used for summary statistics. Fractional numeric values will be presented with a zero to the left of the decimal point (for example, 0.12 – 0.30).

2.2 DEFINITIONS OF ANALYSIS POPULATIONS (ANALYSIS SETS)

2.2.1 Safety Population

The safety population will consist of all participants who received at least one dose of study drug (IV FCM).

2.3 DEFINITIONS AND CONVENTIONS FOR DATA HANDLING

2.3.1 Baseline Definition

For evaluations collected at multiple time points, the baseline will be defined as the last value obtained before the first dose of study drug.

2.3.2 Study Day

Study Day will be calculated relative to the day of first dose (defined as Day 1).

If the assessment (or event) date falls on or after the date of first dose then

$$\text{Study Day} = \text{Assessment Date} - \text{Date of First Dose} + 1$$

If assessment date falls before the date of first dose then

$$\text{Study Day} = \text{Assessment Date} - \text{Date of First Dose}$$

In the case of adverse events or concomitant medications where the assessment date is partially or completely missing, Study Day and any corresponding durations will follow the conventions given in Section 2.3.4.

2.3.3 Time Windows for Analysis

No assessment windows will be defined for the purpose of classifying measurement obtained outside scheduled assessment times. The summary by visit will be based on the observations at scheduled visits only. Data from both unscheduled and scheduled will be used for determination of last observed value, and in worst- or best-case changes and/or shifts from baseline.

2.3.4 Handling of Missing Data

A participant who withdraws from the study for any reason will be included in the analyses regardless of time on study. Methods for handling withdrawals and missing data will be specific to each endpoint to be analyzed. Missing data will not be imputed for descriptive statistical summaries in safety or efficacy.

For statistical inferential (paired t-tests) analyses, missing data will be imputed using last observation carried forward (LOCF) method for hemoglobin and other efficacy endpoints. e.g. for primary endpoint, hemoglobin, when Day 35 data is missing (subject has discontinued before Day 35, or measurement not taken at Day 35 though subject was not discontinued), Day 28 or last unscheduled result will be carried forward. If there is no post-baseline value observed, the worst value obtained from Day 35 of all subjects in the safety population will be used. The worst value is defined as the lowest value for hemoglobin, ferritin, TSAT and reticulocyte hemoglobin content.

Dates missing the day or both day and month of the year will adhere to the following conventions to classify TEAE and to classify prior/concomitant medications.

- A medication with a completely missing start date will be considered a prior medication. A medication with a completely missing stop date will be considered a concomitant medication.
- If complete AE onset date is missing and AE end date is on or after the first dose date then it will be counted as a treatment emergent AE (TEAE) for the study. If complete AE onset date is missing and AE end date is before the first dose date then it will not be counted as a TEAE for the study.
- If an AE or a medication has a partial missing start or stop date, the following rules will be used for imputation:
 - If year is present but month and day are missing, impute start date as January 1 of that year or first dose date if the year is the same as the year of first dose date and impute stop date as December 31 of that year.
 - If year and day are present but month is missing, impute start month as January or the month of the first dose date if the year is the same as the year of first dose date and impute stop month as December.
 - If year and month are present but day is missing, impute start date as first day of that month or first dose date if the year and month are the same as the year and month of first dose date and impute stop date as last day of that month.

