8.5.2. Adverse Events

Adverse events will be coded by system organ class (SOC) and preferred term (PT) using the Medical Dictionary for Regulatory Activities (MedDRA) dictionary.

The number and percent of participants who report treatment emergent AE (TEAE) will be summarized. A TEAE is an event with onset date on or after the study drug start date.

Adverse event summaries will exclude preferred terms that describe asymptomatic serum ferritin, TSAT, and reticulocyte values (or changes). This approach is justified by the reporting of these values in efficacy summaries and is consistent with the protocol-defined reporting standards for Hgb/hematocrit (Hct) and low iron indices. For the purposes of this study, non-serious anemia (Hgb or Hct below the normal range or worsened from baseline) or iron deficiency (iron indices below the normal range or worsened from baseline) will not be considered adverse events. Anemia or iron deficiency will be considered end points if an intervention is required.

The adverse event profile will be characterized with severity (as graded by the NCI-CTCAE) and relationship (unrelated and related) to study drug. Related adverse events will be events that are possibly or probably related to treatment in the investigator's judgment.

Participants who report the same preferred term on multiple occasions will be counted once for the preferred term: under the highest severity when summarized by severity and under the closest relationship to study drug when summarized by relationship. If a participant reports multiple preferred terms for a SOC, the subject will be counted only once for that SOC.

The number and percent of participants who report treatment-emergent serious adverse events will be similarly summarized for each treatment group. The number and percent of participants who report treatment-emergent adverse events resulting in discontinuation of study drug will be similarly summarized for each treatment group.

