7.1 ADVERSE EVENTS

Adverse events (AEs) will be coded by System Organ Class (SOC) and Preferred Term (PT) using the Medical Dictionary for Regulatory Activities (MedDRA) dictionary. Adverse event

summaries will exclude preferred terms that describe asymptomatic serum ferritin, TSAT, and reticulocyte values (or changes). This approach is justified by the reporting of these values in efficacy summaries and is consistent with the protocol-defined reporting standards for hemoglobin/hematocrit and low iron indices. For the purposes of this study, non-serious anemia (hemoglobin or hematocrit below the normal range or worsened from baseline) or iron deficiency (iron indices below the normal range or worsened from baseline) will not be considered adverse events. Anemia or iron deficiency will be considered end points if an intervention is required.

A treatment-emergent adverse event (TEAE) is defined as an event with onset date on or after the study drug start date. Partial date TEAE classification rules refer to Section 2.3.4. Only TEAEs will be included in summary tables.

The incidence of TEAEs will be summarized as the number (percentage) of subjects with TEAEs within SOC and PT. Subjects who report the same PT on multiple occasions will be counted once for the PT: under the highest severity (severe > moderate > mild) CTCAE when summarized by severity and under the closest relationship (probably related > possibly related > unlikely related > none) to study drug when summarized by relationship. If a subject reports multiple PT for a SOC, the subject will be counted only once for that SOC. Events with unknown severity or relationship will be counted as unknown.

TEAEs will be summarized as below.

- An overview table, including number of subjects with
 - TEAEs
 - serious TEAEs
 - study drug related TEAEs
 - study drug related Serious TEAEs
 - TEAEs by severity
 - TEAEs leading to study drug discontinuation or withdrawal from study
 - TEAEs leading to death
- TEAE by SOC
- TEAE by PT
- TEAE by SOC and PT
- TEAE by SOC, PT, and Severity (CTCAE)
- Study drug related TEAEs by SOC, PT
- Serious TEAEs by SOC and PT
- Study drug related serious TEAEs by SOC and PT

- TEAEs leading to study drug discontinuation or withdrawal from study by SOC and PT
- TEAEs leading to death by SOP and PT

Unless otherwise stated, all TEAE tables will be sorted by SOC and PT in decreasing frequency of the number and percentage of subjects.

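### Adverse events with missing causality leave the drug-related tables with no count shown, and an ongoing event with no onset date has no treatment-emergence rule

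*SAP*

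**What the plan says.** - **General rule, SAP 2.3.4.** "Missing data will not be imputed for descriptive statistical summaries in safety or efficacy". This sentence mentions neither causality nor treatment-emergence, and the same section goes on to impute partial dates. The text that decides the matter is below.
- **Missing causality, SAP 7.1.** "Events with unknown severity or relationship will be counted as unknown". Protocol 8.5.2 defines the other side: "Related adverse events will be events that are possibly or probably related to treatment in the investigator's judgment". The SAP 7.1 output list contains entries such as "Study drug related TEAEs by SOC, PT" but no table that splits TEAEs by relationship category. Where a child has several records of one preferred term, the closest relationship is taken in the order probable, possible, unlikely, none.
- **Missing onset, SAP 2.3.4.** The first rule makes the event a TEAE: "If complete AE onset date is missing and AE end date is on or after the first dose date then it will be counted". Under the second rule, an event that ended before the first dose is not a TEAE. There is no third rule.
- **Definition and filter, SAP 7.1.** "A treatment-emergent adverse event (TEAE) is defined as an event with onset date on or after the study drug start date". Then: "Only TEAEs will be included in summary tables".
- **Collection, protocol 7.1 to 7.3.** Sites record onset, relationship and resolution, and may mark an event as unresolved in place of a resolution date. Non-serious and serious events are both collected from first treatment with ferric carboxymaltose.

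**The concern.** Safety is part of the primary objective of a small, single-arm, open-label study with no data and safety monitoring board. Two kinds of incomplete record are handled in a way that can lower a reported harm count.

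An event whose causality field is blank is not possibly or probably related, so it falls outside the related counts. Because no listed table shows an unknown category, a reader of the related-TEAE table cannot tell that an assessment was missing.

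An ongoing event with no onset date satisfies neither missing-onset rule. A program written literally from the onset-based definition would find no qualifying date and could leave the event out of every TEAE table, including the serious and fatal ones. The collection window indicates that such an event arose on treatment.

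**Working it through.** The documents give no figure on this point to reproduce, so the check is a reading of the rules followed by a sizing.

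**1. Where a TEAE with missing causality appears** (counted from the lists in SAP 7.1 and 7.1.1)

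| Output group | Listed | Restricted to related | Event still appears in |
|---|---|---|---|
| Overview rows | 7 | 2 (related; related serious) | up to 5 |
| TEAE tables | 9 | 2 (related; related serious) | up to 7 |
| Special-interest tables | 3 | 0 | up to 3 |

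The event is lost only from the related outputs. It remains in the all-TEAE, severity, serious, discontinuation, death and special-interest outputs wherever it qualifies for them.

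The relationship order has four levels and none is for unknown. A child with one record of none and one blank record for the same term is outside the related tables wherever unknown is placed. A child with one possible and one blank record is inside. The missing level therefore does not change any table now listed, but it leaves any summary by relationship category undefined.

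**2. Treatment-emergence by onset and end date** (SAP 2.3.4 and 7.1)

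| Onset date | End before first dose | End on or after first dose | Ongoing, no end date |
|---|---|---|---|
| On or after first dose | TEAE | TEAE | TEAE |
| Before first dose | Not TEAE | Not TEAE | Not TEAE |
| Year only, same year as first dose | TEAE (set to first-dose date) | TEAE | TEAE |
| Completely missing | Not TEAE | TEAE | **No rule** |

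Of these 12 combinations, one has no rule. SAP 2.3.4 does say what to do with a medication that has no stop date (treat it as concomitant), but has no matching sentence for adverse events.

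**3. Size.** The only input from the documents is the maximum of about 36 participants (protocol 8.5.6, SAP 1.3.3). The number of children whose only qualifying event is affected, k, is not given; k = 1 to 3 is assumed.

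- Shift per child = 1/N = 1/36 = 2.8 percentage points. Because 36 is a maximum, the shift is larger if fewer are treated; for an assumed N of 20 it is 1/20 = 5.0 points.
- Exact (Clopper-Pearson) 95% intervals at N = 36: 0/36 = 0% (0 to 9.7%); 1/36 = 2.8% (0.1 to 14.5%); 3/36 = 8.3% (1.8 to 22.5%).

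If a category would otherwise show zero, restoring one child moves the upper limit from 9.7% to 14.5%.

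**The case against.** The strongest case on the other side is that both situations should be rare. Onset and relationship are expected entries on the adverse event page, events are assessed at every visit from Day 0, and the study lasts 35 days. For the onset gap to arise, even the year must be missing and the event must have no end date. This stands, and it is the main reason for grading the point as minor.

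It can also be said that SAP 2.1 permits unknown data to be shown as a separate category and promises the ICH-required listings, and that protocol 8.5.2 plans to describe events by relationship. That is true, but the SAP 2.1 wording is permissive, the protocol's relationship split has only related and unrelated, and no listed table carries the unknown count.

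Finally, counting a blank as related departs from a definition based on the investigator's judgment. That stands too, and it is why the fix needs a footnote from which the judgment-only count can be recovered.

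Several stronger readings are tempting, and the documents do not support them:

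- *That both kinds of event vanish from the harm tables.* Events with unknown causality leave only the related outputs counted above.
- *That the SAP excludes undated ongoing events.* It is silent. Omission is an inference from the definition and the filter, and the collection window points the other way.
- *That the bias is always downward.* If the true causality is none or unlikely, or the child has another related TEAE, the child-level related count is not understated.
- *That these rules break a uniformly conservative convention.* There is none: a medication with no start date is classed as prior, and the missing-month rule can place an onset before the first dose.
- *That a relative understatement can be quoted.* Going from 4/36 (11.1%) to 3/36 (8.3%) is a 25% fall only because 4 was assumed; the relative loss is 1 divided by the unknown starting count.
- *That early leavers will have the incomplete records.* Protocol 7.1 permits telephone follow-up but says nothing about completeness, and protocol 6.3.5 asks for the Day 35 procedures before exit.

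**Conclusion.** The point holds in limited form and is minor. By stated rule, a TEAE with missing causality is outside the related outputs, and no listed table discloses how many there are. By omission, an ongoing event with no onset date has no treatment-emergence status and could be dropped by a literal program.

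The effect is up to 2.8 percentage points per affected child if 36 are treated, and zero if no record is incomplete. This assumes that the affected event is the child's only one qualifying for the count in question. For causality, an understatement also requires that the event would have been judged possibly or probably related.

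**What to change.** Two changes to the SAP:

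- **Section 2.3.4:** count an adverse event with a completely missing onset date as a TEAE unless a known end date is before the first dose. Both existing outcomes stay the same; only the empty cell is filled.
- **Section 7.1:** count a TEAE with missing relationship as related in the overview and in the related and related-serious tables, and treat it as related in the closest-relationship ranking. Add a footnote giving the number so classified, so that the count based on the investigator's judgment alone can be recovered.

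The cost is two sentences, a footnote and minor programming. The downside is that the related-TEAE percentage may be slightly less favourable and could overstate relatedness for those few records.

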6.1 PRIMARY EFFICACY ANALYSIS

6.1.1 Change in Hgb from baseline to Day 35

The primary efficacy endpoint is the change in Hgb from baseline to day 35. The actual value of Hgb on baseline, Day 35, and change from baseline to Day 35 will be summarized via descriptive statistics.

The change in Hgb from baseline to Day 35 will be assessed using paired t-tests (two-sided test, $\alpha=0.05$). Baseline Hgb will be defined as the last Hgb obtained before the first dose. Missing value will be imputed using LOCF as specified in Section 2.3.4.

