6.2 SECONDARY EFFICACY ANALYSES

6.2.1 Change in ferritin from baseline to Day 35

The actual value of ferritin on baseline, Day 35, and change from baseline to Day 35 will be summarized via descriptive statistics.

The change in ferritin from baseline to day 35 will be assessed using paired t-tests (two-sided test, $\alpha=0.05$). Baseline ferritin will be defined as the last ferritin obtained before the first dose. Missing value will be imputed using LOCF as specified in Section 2.3.4.

6.2.2 Change in TSAT from baseline to Day 35

The actual value of TSAT on baseline, Day 35, and change from baseline to Day 35 will be summarized via descriptive statistics.

The change in TSAT from baseline to day 35 will be assessed using paired t-tests (two-sided test, $\alpha=0.05$). Baseline TSAT will be defined as the last TSAT obtained before the first dose. Missing value will be imputed using LOCF as specified in Section 2.3.4.

6.2.3 Change in Hgb, ferritin, TSAT and Reticulocyte Hemoglobin Content from baseline throughout the Study

The actual value of Hgb, ferritin, TSAT and reticulocyte hemoglobin content (CHr) on baseline, each post-baseline visit (Day 7, 14, 28 and 35), and change from baseline to each post-baseline visit will be summarized via descriptive statistics.

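### A child with no post-baseline value is given another child's lowest Day 35 level, but the t-tests use change from own baseline, so the worst value can be a gain or an outsized loss

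*SAP*

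**What the plan says.** SAP 2.3.4 keeps every treated child in the analysis: "A participant who withdraws from the study for any reason will be included in the analyses regardless of time on study". Descriptive summaries are not imputed. For the paired t-tests, a missing Day 35 value is replaced by the last earlier post-baseline result. A child with no such result falls to a second rule: "If there is no post-baseline value observed, the worst value obtained from Day 35 of all subjects in the safety population will be used". The next sentence fixes the meaning: "The worst value is defined as the lowest value for hemoglobin, ferritin, TSAT and reticulocyte hemoglobin content".

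The tests themselves are on within-child change. For the primary endpoint, SAP 6.1.1 states: "The change in Hgb from baseline to Day 35 will be assessed using paired t-tests". SAP 6.2.1 and 6.2.2 say the same for ferritin and TSAT. In SAP 2.3.1, "the baseline will be defined as the last value obtained before the first dose of study drug", so each child is compared with his or her own starting value.

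SAP 6.1.1 describes the imputation only as LOCF: "Missing value will be imputed using LOCF as specified in Section 2.3.4". SAP 9 lists LOCF as a departure from the protocol and does not mention the cross-subject rule. No sensitivity analysis is planned.

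**The concern.** The fallback is defined on the level scale and the test is on the change scale. Once another child's minimum is put in, the imputed change depends on two unrelated numbers: how low that other child happened to be, and how low this child was at baseline. A severely anaemic child may be credited with a gain that nobody measured. A child near the entry limit may be charged with a loss much harsher than no response. The rule is therefore not reliably the worst case on the scale being tested, and it is not last observation carried forward either.

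At stake are the p-values for Hgb, ferritin and TSAT, and any confidence interval computed from the imputed data. CHr is named in the rule, but no t-test is planned for it.

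**Working it through.** The plan has no figure to reproduce: SAP 1.3.3 says that no sample size was estimated, and no SD, expected rise or dropout rate is given.

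**Inputs from the documents.** At most about 36 children (SAP 1.3.3). Hgb below 11 g/dL, ferritin up to 300 ng/mL and TSAT below 30% at entry, with no lower limits (Protocol 4.2.1). Two-sided alpha 0.05 (SAP 6.1.1). Analysis set: everyone with at least one dose (SAP 2.2.1). All other inputs are assumptions.

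**Step 1: the imputed change.** Imputed change = m - b, where m is the lowest Day 35 level in the group and b is the child's own baseline. The shift in the trial mean, relative to zero change for that child, is (m - b)/36.

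| Variable | m | b | m - b | Shift in mean |
|---|---|---|---|---|
| Hgb, g/dL | 9.0 | 7.0 | +2.0 | +0.06 |
| Hgb, g/dL | 9.0 | 10.9 | -1.9 | -0.05 |
| Ferritin, ng/mL | 60 | 8 | +52 | +1.4 |
| Ferritin, ng/mL | 60 | 300 | -240 | -6.7 |

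The values of m are assumed. All four baselines satisfy the entry limits.

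**Step 2: the t statistic.** Assume 35 observed Hgb changes with mean 1.0 and SD 1.0, plus one child with b = 10.9 while m = 8.0, so m - b = -2.9.

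- Zero change: mean = 35/36 = 0.97, SD 1.00, t = 0.972/(1.00/6) = 5.84.
- SAP rule: mean = (35 - 2.9)/36 = 0.89, SD 1.18, t = 0.892/(1.181/6) = 4.53.

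The conclusion is the same. With 11 observed children plus one (36 is only a maximum), zero change gives mean 11/12 = 0.92 and p = 0.009. The SAP rule gives (11 - 2.9)/12 = 0.68 and p = 0.14.

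**Step 3: simulated Hgb tests.** 40,000 trials per setting, 36 children, of whom 1, 2 or 3 have no post-baseline value. Baseline is normal (9.6, SD 1.0) cut below 11, which gives mean 9.44 and SD 0.86. Day 35 = mean + rise + slope x (baseline - mean) + residual. At slope 1.0 the SD of change equals the residual SD. Chance of p<0.05 with 1 / 2 / 3 such children:

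| Slope | Residual SD | Rise | SAP rule | Observed cases |
|---|---|---|---|---|
| 1.0 | 1.0 | 0 | 5.1 / 8.0 / 13.9% | 5.0% |
| 1.0 | 1.0 | 0.5 | 60 / 38 / 22% | 82 / 81 / 80% |
| 1.0 | 0.7 | 0.5 | 88 / 65 / 42% | about 98% |
| 0.5 | 1.0 | 0.5 | 60 / 43 / 29% | 75 / 74 / 73% |
| 1.0 | 1.0 | 1.0 | 99.8 / 98.4 / 93.8% | 100% |
| 1.0 | 1.0 | 2.0 or more | 100% | 100% |

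With no true change, the excess over 5% consists of false losses. Zero change gave p<0.05 as often as observed cases, to within about 0.1 percentage point. The reason is that added zeros leave the sum and the sum of squares of the changes unchanged.

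Mean change in g/dL, slope 1.0, SD 1.0, two such children:

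| Rise | Observed | SAP rule | Zero change | Smaller of the two |
|---|---|---|---|---|
| 1.0 | 1.00 | 0.84 | 0.94 | 0.84 |
| 2.0 | 2.00 | 1.84 | 1.89 | 1.83 |
| 3.0 | 3.00 | 2.84 | 2.83 | 2.81 |

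**Step 4: how often the worst value is a gain.** For Hgb with one such child, over slopes 1.0 and 0.5 and residual SDs 0.7 and 1.0: 5-22% at a rise of 1.0, 22-58% at 2.0 and 54-91% at 3.0.

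For ferritin with two such children (independent lognormals, log-SD 1.0 at baseline, limited to 300, and 0.6 at Day 35), by baseline and Day 35 medians: 90% for 15 to 200, 99% for 8 to 300, but 24% for 30 to 50. For TSAT with two such children (log-SD 0.5, limited to 29.9%, and 0.4): 92% for 6% to 30%, but 13% for 12% to 15%.

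**The case against.** The strongest reply is that the rule will hardly ever be used and errs on the safe side when it is. Blood is drawn at Days 7, 14, 28 and 35 (Protocol 3.3). Children who stop study drug are asked to keep the visit schedule (Protocol 4.5). Day 35 procedures are to be done at early exit (Protocol 6.3.5). Nothing in the documents suggests two or three such children among 36. The large power losses also need a true rise of about 0.5 g/dL, and the plan itself calls a rise below 1 g/dL on oral iron unsatisfactory. The Step 1 baselines lie in the tails: under the assumed Hgb distribution, 7.0 or lower has a probability of about 0.5%.

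A harsh value is also what a worst-value rule is meant to supply. With no true change (SD 1.0), false gains occur in 0.7 / 0.2 / 0.1% of trials under the SAP rule and in about 2.5% under zero change. For the Hgb p-value, zero change is practically the same as leaving the child out.

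All of this stands as a limit on size. It does not make the rule coherent. The 2.5% is the nominal one-sided error of a two-sided 5% test, so zero change restores the intended size. A rule that is strict for one child and generous for the next, according to baseline, is not a controlled form of conservatism.

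**Conclusion.** The concern holds. The mismatch between level and change follows from the SAP text alone, and nothing elsewhere in the documents corrects it. For Hgb the usual result at a modest rise is a large imputed loss. For ferritin and TSAT, when the response is strong, it is usually a credited gain.

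The effect is limited. It reaches only the inferential results, and in every setting simulated the mean stayed below the observed-case mean, so the rule does not flatter the drug on average against observed cases. With about 36 children it alters the Hgb test materially only if the true rise is small, and it matters more if far fewer children enrol. These sizes rest on assumed distributions, rises and counts of affected children. The change is worth making before database lock but is not critical.

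**What to change.** In SAP 2.3.4, replace the worst-value rule. For a treated child with no post-baseline value, set the change to zero in the paired t-tests, which carries the child's own baseline forward. This keeps the child in the analysis, as 2.3.4 promises. It also fits the LOCF label in SAP 6.1.1 and SAP 9, because the baseline is that child's last observation. Leave LOCF unchanged for children who have a post-baseline value.

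Add two sensitivity analyses: (1) for such a child, the smaller of zero and the change given by the current rule; (2) the observed-case paired t-test. Report the number of children to whom the rule was applied, by endpoint.

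The cost is one sentence of SAP text and two re-runs of the same test on data already collected. The drawback is that zero change is still a single imputation and is usually less strict than the current rule for Hgb (0.94 against 0.84 g/dL at a true rise of 1.0, two of 36 children). Sensitivity analysis (1) covers this, returning 0.84 in that setting.
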